#### ETHICAL CONSIDERATION

The study will only be commenced after appropriate approval from the Institutional review board is obtained. Informed consent will be obtained from all the participants of this study after the study has been explained in details to them by a member of the team who will be at least a Senior resident that has been trained on the protocol of the study before the commencement of the study. The aims and objectives of the study will be explained to every potential study participant as well as the method of selection. They will be educated about the method of group assignment and the details of the technique inserting chest tube and the different plans of managing the thoracostomy wound indicating the possible complications of wound infection, wound breakdown, iatrogenic pneumothorax, need for frequent dressings, post-procedural pain and increased analgesic requirements as well as need for chest tube re-insertion. The patients will be reassured of the safety of the chest tube insertion procedure. After group assignment by the research assistant, the patient will be informed of the assigned group and requested to complete the informed consent form to authorize the surgeon to proceed with the procedure as per the protocol described above.

The process of obtaining the informed consent will be individualized, the patient or the guardian will be reassured that the information obtained will be protected and not disseminated. Also, the patient will be informed that the decision to participate or decline participation in the study will not affect the quality of treatment that will be offered to them.

The benefit of the study will be explained to them because it will contribute to the knowledge of in management of patients. The findings may also help surgeons in determining when to use purse strings in management of chest tubes. Also, for patients it will help reduce complications related to chest tube insertion and management.

Suturing with U-Technique versus Un-Reapproximated wound Edges during removal of Closed Thoracostomy-tube drain - A single centre Open-label prospective randomized trial (SUTURE TRIAL)

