#### **STUDY SUMMARY**

Title: Suturing with U-Technique versus Un-Reapproximated wound Edges during removal of Closed Thoracostomy-tube drain - A single centre Open-label randomized prospective trial (SUTURE TRIAL)

**Background:** Closed thoracostomy tube drainage or chest tube insertion is one of the most commonly performed procedures in thoracic surgery. There are several published evidence-based guidelines on safe performance of a chest tube insertion. However, there is absence of prospective controlled trials or systematic reviews indicating the safest technique of closing the wound created at the time of chest tube insertion and that best guarantees good wound and overall outcomes, post-chest tube removal. The use of a horizontal mattress non-absorbable suture or U- suture which is placed at the time of chest tube insertion and used to create a purse-string wound re-approximation at the time of tube removal has been an age-long and time-honored practice in most thoracic surgical settings. It has been established by a recent study that an occlusive adhesive-absorbent dressing can also be safely used to occlude the wound at the time of chest tube removal with good wound and overall outcomes though the study focused on tubes inserted during thoracic surgical operations.

Research Design: The study is an Open-label randomized prospective trial

**Methodology:** 142 consenting patients with indication for chest tube insertion, who meet the inclusion criteria for enrolment in the study will be randomly assigned into two balanced groups- Group A; that will have a Prolene 1 purse-string suture placed around the thoracostomy wound at the time of chest tube insertion and which will be used for the thoracostomy wound closure at the time of chest tube removal and Group B, that will not have a purse-string suture placement during chest tube insertion and will have their wounds covered by an occlusive adhesive-absorbent dressing material (Primapore\*), at the time of chest tube removal care and outpatient follow-up; will be similar for both groups and will follow a pre-determined standardized protocol. Specific clinical outcomes while the chest tube is indwelling and specific clinical and wound outcomes after the chest tube removal will be observed in both Groups for comparison and to determine causal relationships. Observations will be recorded in a specially-designed study proforma.

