# SAMPLING AND RANDOMISATION TECHNIQUES

A block but balanced randomization technique (Unstratified) will be used in determining the use or otherwise of purse-string in the study population. Randomization and intervention assignment into either of the two groups A or B (purse string versus non-purse string) will be determined by grouping labels (A or B) and serialization generated by the soft-ware Winpepi from number 1 to 142 (i.e. Random assignment of 71 in Group A and 71 in Group B).

The generated sequence will be stored on the computer of a blinded research assistant who will be required to inform the team of the next assigned intervention according to the generated sequence, at the time of chest tube insertion for all included and consenting patients. The research assistant will keep record of all assigned labels and ensure all intervention assignment follows the computer-generated sequence in an uninterrupted and reproducible manner.

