### PROCEDURE DETAILS AND DATA COLLECTION TECHNIQUES

#### 1) Before Chest Tube Insertion

In all formally consenting patients who have met the indications for chest tube insertion and participation in this study, the chest tube will be inserted under aseptic techniques. This can be done in the ward at the patient's bedside or in the theatre for post-thoracotomy patients. All chest tube insertion will be performed by the principal investigator or any senior resident doctor in thoracic surgery who has been duly trained to perform this procedure following standard protocols and techniques. The step-by-step guide on how to safely insert a chest tube using the procedural details provided below will be printed out and mastered by all surgeons involved in this study with strict observance of all the required techniques and steps.

As discussed above, a start dose of intravenous third generation cephalosporin antibiotic will be administered prior to the procedure. 1g of Ceftriaxone will be used in this regard in compliance with current practice protocol.

Prior to commencement of the procedure and after formal consent by the patient. The research assistant will be contacted to provide the assigned group for that patient using the computer generated sequence obtained with the WINPEPI software at the beginning of the study.

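### The protocol gives two orders for consent and allocation, and under one of them the patient completes the consent form already knowing the arm

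*Combined protocol and SAP*

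**What the plan says.** All sections cited are in the combined protocol and SAP.

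- **Ethical Consideration** opens by tying consent to the explanation of the study: "Informed consent will be obtained from all the participants of this study after the study has been explained in details to them". Later in the same paragraph it sets out a sequence: "After group assignment by the research assistant, the patient will be informed of the assigned group and requested to complete the informed consent form". The purpose given for that form is "to authorize the surgeon to proceed with the procedure as per the protocol described above". The next paragraph tells patients that "the decision to participate or decline participation in the study will not affect the quality of treatment that will be offered to them".
- **Procedure Details, 1) Before Chest Tube Insertion** gives the order as: "Prior to commencement of the procedure and after formal consent by the patient. The research assistant will be contacted to provide the assigned group".
- **Sampling and Randomisation Techniques** has the assistant disclose the next assignment "at the time of chest tube insertion for all included and consenting patients". The assistant also keeps a record of the labels and must "ensure all intervention assignment follows the computer-generated sequence in an uninterrupted and reproducible manner".
- **Study Summary**, Methodology, says "142 consenting patients with indication for chest tube insertion, who meet the inclusion criteria for enrolment in the study will be randomly assigned" to the two groups.
- **Data Analysis and Management** plans a Cox analysis adjusted for potential confounders. It names no analysis population and does not say how a patient who refuses after allocation is counted.

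**The concern.** Random allocation protects the comparison only if the decision to enter the trial is made before the arm is known. This holds in an open-label trial too: treatment cannot be masked here, but the next assignment can be withheld until the patient is enrolled, and the procedural section already arranges for that.

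The ethics section reverses the order. If the signed form is what makes someone a participant, a patient who prefers one closure method can decline on learning that the other was assigned. The protocol gives patients grounds for a preference. Its Problem Statement links the purse-string to pain, infection, suture removal and poor scarring, and links occlusive dressing without sutures to more pneumothorax and dehiscence. Possible complications are to be explained during the consent discussion. If those who decline one arm differ in risk from those who decline the other, the groups compared no longer differ by chance alone.

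**Working it through.** The point depends on the order of steps and not on a figure, so there is no planned number to reproduce. The check is a comparison of texts.

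**Step 1: order in each section**

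| Section | First | Second | Express or implied |
|---|---|---|---|
| Before Chest Tube Insertion | Formal consent | Group requested | Express |
| Sampling and Randomisation Techniques | Patient is included and consenting | Group disclosed | Implied |
| Study Summary | Patient is consenting and eligible | Random assignment | Implied |
| Ethical Consideration | Group assigned and disclosed | Consent form completed | Express |

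One express statement is contradicted by another. Two further sections agree with the procedural order, but only because they describe the patients being assigned as consenting.

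**Step 2: can both express statements be true?** Only if there are two acts of consent: study consent before the group is requested, and a later authorisation of the procedure. The stated purpose of the later form, authorising the surgeon, is compatible with that. However, the section calls it the informed consent form, and no section describes two steps or a different document signed earlier. The form itself is not in the copy reviewed, so it can neither confirm nor rule out this reading.

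**Step 3: what follows if the ethics wording governs?** The patient knows the arm and has been told that declining is allowed. Enrolment can then depend on the arm.

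**Step 4: would the plan reveal or correct this?** In part.
- The label record would allow refusals to be traced to an arm, and the uninterrupted sequence favours labels being used in order.
- The Study Variables and Study Proforma sections collect comorbidity, smoking, body mass index and other baseline factors. Selection acting through these could show in the baseline comparison and be partly adjusted for.
- Selection through reasons that are not recorded could not be adjusted for. The proforma records whether a purse-string was used, but no field visible in it records a refusal or its reason.

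**Step 5: size.** A figure would need the refusal rate after disclosure in each arm and the relation between refusal and outcome risk. The documents give neither. The 5% non-response allowance in the Sample Size section is not defined as refusal and is not tied to arm or risk, so it cannot stand in for them.

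**The case against.** The strongest reply is that most of the text already has the right order. The procedural section is the one staff will work from, and two other sections are consistent with it. A single sentence in the ethics section departs from it, and that sentence describes a form authorising the surgeon. The same section has the study, the method of assignment and both wound plans explained beforehand. Since consent pages were removed from the review copy, the absence of a described two-step process is weak evidence that none exists.

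Much of this stands. It makes the harmful reading less likely, and it is why the consequence is stated conditionally. It does not remove the conflict: two current sections give opposite orders, and the one on consent is where staff would look to learn when the form is signed. If two steps are intended, one sentence would settle the matter.

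It is also fair to say that part of the safeguard exists already, since the label record and the uninterrupted sequence are required. What is missing is how refusals after allocation are reported and analysed.

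**Conclusion.** The point holds as an internal contradiction that should be fixed. Confidence is high that the wording conflicts. The bias is conditional: it needs staff to follow the ethics wording, the form to be the study consent, some patients to decline because of the arm, and those refusals to be related to outcome risk. Its size and direction are unknown, and it is zero if refusal is unrelated to risk.

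A reader might infer three stronger things that the documents do not support.

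- **That surgeons may turn down an allocation they dislike.** No section allows this. The freedom to decline is given to the patient, and assignment must follow the sequence without interruption.
- **That the bias would be a known share of the planned difference, or would raise the false-positive rate above 5%.** Any such figure would rest wholly on assumed risk and refusal rates.
- **That the adjusted analysis is useless against this.** It could partly deal with selection through recorded baseline factors. It cannot reach reasons that are not recorded.

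**What to change.** 1. **Ethical Consideration:** reword so that written study consent, covering both possible groups, is completed before the research assistant is contacted, in line with Before Chest Tube Insertion. If a later authorisation of the procedure is intended, state that it is separate from study consent.
2. **Data Analysis and Management:** add that every patient whose allocation has been released is reported in the assigned arm, and that refusals after allocation are reported by arm with reasons. The label record already required under Sampling and Randomisation Techniques can serve as the source, with the reason for refusal noted beside the label.

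The cost is a short amendment to two sections, with no added patients or procedures. The downside is that patients who change their mind on hearing the group will appear as withdrawals after randomisation. That makes the losses visible, which is preferable to having them disappear before enrolment is counted.

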#### **PROBLEM STATEMENT**

In spite of the ubiquitous placement of chest drains for different purposes, there is still a lack of highquality prospectively-designed evidence-based guideline for post-placement management of the chest tubes making current management of patients with chest tubes to be largely reliant on protocols of individual institutions and personal idiosyncrasies mostly borne out of anecdotal experience (13, 14) Several national and international thoracic societies' guidelines exist as well as published literatures that give clear advice on when to consider inserting chest drains (5,7,9). Also, there is a litany of procedural guidelines detailing how to safely perform chest tube insertion. However, there is a paucity of major guidelines or scientifically-proven standard methodology of closing the wound made during the process of chest tube insertion at the time of removal of the chest tube (9,11,15). The conventional method of managing a thoracostomy wound at the time of chest tube insertion is to use an anchoring suture to fix the chest tube to the wound edge thereby preventing it from spontaneously extruding while also placing a purse-string suture around the wound that would be used to close the wound at the time of chest tube removal (2,11). This purse-string suture can also be used as an additional means of securing the chest tube in position with the added advantage of preventing air or pleural fluid from entering or egressing the pleural space (i.e. air and water tightness) during the tube removal process (2). It has been reported that though beneficial for the most parts, this purse-string suture placement at the time of tube insertion has its inherent burden of suture-related pain, irritation and increased rates of wound infection following its placement and retention, an experience reported by patients during the course of the tube drainage and which may persist even after tube removal (11). It means this conventional method can be associated with higher drain removal pain scores and in addition, more frequent outpatient wound dressings after hospital discharge, need for suture removal after the wound has healed and the long-term development of an unsightly thoracostomy scar (2, 11,16). Skin staplers and simple interrupted skin sutures have also been used with equally unsatisfactory wound outcomes (2).

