# STUDY VARIABLES AND DEFINITION

The independent variables to be employed for the analysis include:

- Age of the patient
- Sex of the patient
- Presence of specific co-morbidities (Diabetes, Hypertension, Chronic Liver disease, Chronic kidney disease)
- Charleson Comorbidity Index
- History of cigarette smoking and estimated pack years if positive

- Use of steroids and chemotherapeutic agent
- Abnormal Body mass index (Obesity(BMI> 30kg/m^2), Malnutrition(BMI< 18kg/m^2)

The Dependent variables to be employed for the analysis include:

- Presence of severe pain at the chest tube site after chest tube insertion (Average daily pain score after tube insertion > 5 on the Visual Analog Scale and or Numerical Rating Scale)
- Occurrence of tube dislodgement after chest tube insertion
- Occurrence of peri-tubal leakage of fluid after chest tube insertion
- Presence of wound air suck-in after chest tube removal (indicated by presence of air suck-in sound through the wound into the pleural space during quiet and or forced inspiration)
- Occurrence of wound infection after chest tube removal (presence of purulent or offensive wound discharge with or without fever or presence of wound discharge that is microbiologically positive)
- Occurrence of wound dehiscence after chest tube removal
- Occurrence of early (within 7 days) and late pneumothorax (more than 1 week) after chest tube removal confirmed on chest radiography
- Development of raised or elevated thoracostomy wound scars (unsightly scars appearing like hypertrophic scars or keloids) within 3 months of chest tube removal

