At this stage, for patients in whom a purse-string suture has been assigned to be used (Group A), a size 0 polypropylene suture is used in making the horizontal mattress or U-shaped purse string as illustrated in Figure 3 below.

[figure not shown]

FIGURE 3: Illustration of how the purse-string suture is inserted into the thoracostomy wound

To make this horizontal mattress or U-suture placement or purse-string in the thoracostomy wound, the needle of the suture is inserted from point 1, at 1 cm from the wound edge, through the skin and subcutaneous tissue and then exited through point 2, also 1cm from the wound edge. The needle is then re-inserted through the wound about 2cm along the transverse plane which is point 3. The same motion as performed from point 1 to point 2 is done in a reverse pattern from point 3 to point 4. With this, only the free ends of the suture and the part of the suture between point 2 and point 3 lying on the skin surface will be visible while other parts lie within the thoracostomy wound.

This step of U-suture or purse-string placement will be skipped for all patients assigned to Group B. Thereafter, the blunt dissection is continued with the index finger to the level of the parietal pleura which is breached using the tip of the finger or where the pleural is thickened and fibrotic, with the use of the dissecting forceps. The dissecting finger is introduced into the space to assess for pleural adhesions. As indicated above in the exclusion criteria, all patients with pleural adhesions will be excluded from the study. The intrapleural length of the tube will be estimated from the skin incision to the sternal angle. With the aid of the dissecting forceps, this estimated length of the chest tube with blind-ending external part is then advanced apically and posteriorly into the pleural space.

In both groups, the tube is anchored at the anterior and posterior ends of the wound using size 2 silk sutures placed by narrow horizontal mattress suturing or simple interrupted suturing; to secure the chest tube to the chest wall. For patients in Group A, the placed U-suture or purse-string will be knotted once to create air and water tightness (Figure 4) and the loose ends will also be used to anchor the chest tube by tying the loose ends around the chest for a 2 cm length before making a separate knot on the tube to reinforce the previous silk 2 suture anchorages at both wound ends.

[figure not shown]

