FIGURE 4: Purse string suture tie around the chest tube to achieve air-water tightness. (4)

[figure not shown]
After this, the tube is clamped and connected to either a flutter-valve bag system or an underwater seal drainage system (9). The site is cleaned and dressing is done using sterile gauze with a light paint of 10% povidone iodine followed by application of a firm plaster.

For large pleural effusions or pneumothorax, the drainage is done gradually in a controlled manner to prevent the development of re-expansion pulmonary oedema.

The details of the technical aspects of the operative procedure of chest tube insertion will be observed as described above in those who have been assigned to either groups that are to have the chest tube inserted as an adjunct to a thoracic surgical procedure (i.e. Operative indication).

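### Telling every patient the assigned group before insertion exposes the self-reported tube-phase pain comparison to expectation bias that could be reduced, though not removed

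*Combined protocol and SAP*

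**What the plan says.** The Study Summary declares the design: "The study is an Open-label randomized prospective trial". Under Sampling and Randomisation Techniques the one person described as blinded is the assistant who holds the list, which is "stored on the computer of a blinded research assistant". No masking of patients or of those who collect pain scores is described.

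Ethical Consideration makes disclosure a step of the procedure: "After group assignment by the research assistant, the patient will be informed of the assigned group". The same sentence then asks the patient to complete the consent form so that the surgeon may proceed. The section on the period before chest tube insertion gives a different order: formal consent comes first, and the assistant is contacted for the group afterwards.

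The dependent variables under Study Variables and Definition include "Presence of severe pain at the chest tube site after chest tube insertion", defined as "Average daily pain score after tube insertion > 5 on the Visual Analog Scale and or Numerical Rating Scale". The section on indwelling tubes has pain intensity assessed at least twice a day on ward rounds, with three self-report scales. The Problem Statement gives the direction of the authors' expectation, ascribing to the purse-string an "inherent burden of suture-related pain, irritation and increased rates of wound infection following its placement and retention".

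On what the patient could see while the tube is in, the insertion section says "In both groups, the tube is anchored at the anterior and posterior ends of the wound using size 2 silk sutures", and afterwards the "dressing is done using sterile gauze with a light paint of 10% povidone iodine followed by application of a firm plaster", with no difference by arm. Group A also receives a polypropylene U-suture.

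**The concern.** Pain on a rating scale is the patient's own judgement, and it can move with what the patient believes was done. Here every patient learns the arm before giving the first score. Each has also been taught about both wound-management plans and warned that pain may follow. If patients with a retained suture expect it to hurt and score accordingly, the tube-phase comparison mixes the effect of the suture with the effect of knowing about it.

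The comparison of tube-related complications while the drain is in place is one of the three specific objectives, and severe tube-site pain belongs to that phase. There may also be a knock-on effect. The follow-up section has analgesia escalated when the score exceeds 5, so scores driven by expectation could make analgesic use differ between arms as well.

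**Working it through.** **1. Can patients be kept unaware while the tube is in?** The protocol's own descriptions, side by side:

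| Feature until removal | Group A | Group B | Source |
|---|---|---|---|
| Silk anchor sutures at both wound ends | yes | yes | During chest tube insertion |
| Gauze, povidone iodine, firm plaster | yes | yes | During chest tube insertion |
| Polypropylene U-suture, partly on the skin surface | yes | no | During chest tube insertion |
| Ends of that suture tied over 2 cm and knotted on the tube | yes | no | During chest tube insertion |
| Site uncovered for daily dressing | yes | yes | Management of indwelling chest tubes |
| Adhesive dressing (Primapore) versus tied suture | only at removal | only at removal | Procedure for chest tube removal |

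The conspicuous contrast between arms appears only at removal. Before that, the difference is one additional suture at a site that already carries sutures and lies under a common dressing. A lay patient may not recognise the arm unless told. Some will: part of the suture shows, the dressing comes off daily, and bedside insertion is done under local anaesthesia with the patient awake.

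**2. How large could the effect be?** The plan gives no pain rate, no standard deviation and no sample-size figure for pain, so there is nothing of its own to reproduce. What follows is an illustration.

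*From the documents:* 71 patients per arm (Sample Size); cut-off above 5 (Study Variables and Definition); 5% significance level (Data Analysis and Management).

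*Assumed:* normally distributed scores; 20% of patients above 5 when there is no bias; SD 2 to 2.5 points; no true difference; knowledge of the arm raises Group A scores by 0.3 or 0.5 point; two-sided two-proportion z test. The plan itself names a Cox analysis for complications, so the test is also a simplification.

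*Formulas.* The biased proportion is p_A = 1 − Φ(0.8416 − shift/SD), where 0.8416 is the normal quantile for 20% in the upper tail; p_B = 0.20. The difference is d = p_A − 0.20. The standard error is SE₀ = √[2p̄(1−p̄)/71] under the null, with p̄ the mean of the two proportions, and SE₁ = √[(p_A(1−p_A) + 0.20×0.80)/71] otherwise. The false-positive rate is Φ[(d − 1.96·SE₀)/SE₁] + Φ[(−d − 1.96·SE₀)/SE₁].

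| Shift | SD | p_A | d | SE₀ | SE₁ | False-positive rate |
|---|---|---|---|---|---|---|
| 0.3 | 2.5 | 0.2353 | 0.0353 | 0.0693 | 0.0692 | 8.0% |
| 0.3 | 2 | 0.2446 | 0.0446 | 0.0698 | 0.0697 | 9.8% |
| 0.5 | 2.5 | 0.2606 | 0.0606 | 0.0707 | 0.0705 | 13.7% |
| 0.5 | 2 | 0.2771 | 0.0771 | 0.0715 | 0.0712 | 18.9% |

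Worked line (0.5, SD 2): 0.8416 − 0.25 = 0.5916, so p_A = 0.2771 and d = 0.0771. Then (0.0771 − 1.96×0.0715)/0.0712 = −0.886, whose normal probability is 0.188. The opposite tail adds 0.001, giving 18.9%.

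Over this range the rate rises from a nominal 5% to about 8-19%.

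**3. How much of that is avoidable?** Only the part that arises from being told. The part that arises from patients noticing the suture, or from cues given by unmasked staff, would remain. The documents give no basis for splitting the two.

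**The case against.** The strongest reply is that the trial is declared open-label and that masking would be incomplete anyway. Group A's suture shows on the skin and on the tube, and the site is exposed every day. Many patients are awake at insertion and have had the technique explained. The doctors on the ward rounds where pain is assessed see the wound and stay unmasked. This stands as a limit on what can be gained. It is not a reason to tell every patient: the open-label label describes the design, and nothing in the documents explains why the person who supplies the pain score must know the arm.

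It can also be said that the direction of expectation is partly assumed. The statement that the suture hurts more is protocol background. The consent text lists pain among possible complications without tying it to one arm, and a patient told that the wound will be left unsutured may worry too. This also stands: the bias could be smaller than illustrated, or mixed in direction.

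A reader might infer that the two arms look identical to the patient, so that full masking is free and the bias wholly needless. The visible suture contradicts this. A reader might also apply the calculation to mean pain scores, where larger shifts give much higher false-positive rates. The plan defines tube-phase pain only as a yes/no outcome, and its research question on pain scores concerns the time after removal, when the arm is evident.

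Finally, the scope is narrow. The list of dependent variables is not ranked, and the sample size rests on acute pneumothorax, which is confirmed by radiograph. Those points are correct and limit the importance of the finding.

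**Conclusion.** The concern holds in a limited form. The protocol requires disclosure of the group before a self-reported outcome is measured, and its own premise supplies a direction for the expectation. A tube-phase difference in severe pain could therefore be due in part to expectation. That is weaker than saying such a difference could not be attributed to the suture at all.

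The size cannot be derived from the documents. The 8-19% range depends on the assumed 20% base rate, SD of 2 to 2.5, shift of 0.3 to 0.5 point and simple test, and non-disclosure would remove only part of it. The point does not extend to pain after removal, to pneumothorax or to the other outcomes that patients do not score. It leaves the planned sample size unchanged. It is worth correcting because the change is cheap, not because the trial's main comparison depends on it.

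**What to change.** - In Ethical Consideration, obtain written consent to either technique before allocation, and delete the step that informs the patient of the group. This also brings the section into line with the order given under the heading on the period before chest tube insertion; the two currently differ.
- Instruct staff not to disclose the group until tube removal.
- Have the patient personally mark the tube-phase pain score.
- Describe the trial as open-label for staff, with patients not told their group while the tube is in.

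The cost is a revised consent paragraph and a staff instruction. No staff, procedures or patients are added. The changed wording needs ethics-board agreement, because disclosure is now built into the step at which the form is signed. Patients would still be fully informed about both techniques. Masking would be partial, would end at removal and would protect only the tube-phase pain comparison. The trial report should say so.
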